ORGANIZATION OF DETAILED PROTOCOL

Title: Boston-Harvard Burn Injury Model System: Cortical modulation with transcranial direct current stimulation (tDCS) for neuropathic symptoms following burn injury.

Protocol #: 2012-p-001996

Date: 03/21/2016

[REDACTED]

[figure not shown]
[REDACTED]

[REDACTED]

[REDACTED]

[REDACTED]

Dysfunction of Neural Pathways in Burn

[REDACTED]

[REDACTED]

[REDACTED]

[REDACTED]

[REDACTED]

[figure not shown]

II. SPECIFIC AIMS

The overall goal for this project is to develop a novel treatment using transcranial direct current stimulation (tDCS) for patients with neuropathic burn symptoms such as pain or itching. Because the interventions to date for this group of patients (mainly drugs) have been marked by limited clinical effectiveness [14], the results of this study will represent an initial, significant step toward providing a new therapeutic alternative to this group of patients. Finally we will also collect neurophysiological data to understand further the mechanistic effects of this novel intervention and compare with the use of tDCS for other chronic pain syndromes.

The following aims will be explored in this study:

Aim 1 - To assess the effects of tDCS treatment on neuropathic symptoms: pain or itching – following burn injury. We will determine the magnitude of pain reduction with the modified Brief Pain Inventory (BPI) and itch severity/activity with the Visual Analog Scale (VAS) and 5-D Scales in active tDCS compared with sham tDCS. *Our first hypothesis is that active tDCS will be associated with a larger pain or itching reduction assessed by BPI and Itch VAS/5-D.*

IV. SUBJECT SELECTION

We will select 60 subjects that have burn injury and meet the following criteria:

Inclusion Criteria:

1. Providing informed consent to participate in the study
2. Age 18 or older
3. Burn injury with pain and/or itch that is moderate to severe (at least 4 on the visual analogue scale during the previous 3 weeks)
4. Burn injury occurred at least 3 weeks prior to enrollment. Patient must be discharged from acute inpatient care. (Patient can be enrolled in either inpatient rehabilitation and/or outpatient care)

Exclusion Criteria:

1. Subjects with burns in scalp in the area of electrode placement (i.e. within 4 cm of the DLPFC and the reference site) as the electrode may cause irritation to the injuries
2. Psychiatric disorders that have led to hospitalization within the past 6 months or signs of suicidality
3. Learning disorders that may affect the patient's ability to complete assessments.
4. Unstable conditions preventing travel to the study site

5. Current use of any anti-epileptic medications or dopaminergic medications known to reduce or inhibit the benefits of tDCS treatment: carbamazepine, oxcarbazepine, phenytoin
6. Contraindications to tDCS including implanted metal plates in the head or implanted brain medical devices
7. Pregnancy
8. History of other neurological conditions associated with structural anatomical changes (i.e. stroke, brain injury, Parkinson's)

[Redacted]

[Redacted]

[Redacted]

[Redacted]

[Redacted]

[Redacted]

[Redacted text block]

[Redacted text block]

[Redacted text block]

[Redacted text block]

[Redacted text block]

[Redacted text block]

[Redacted text block]

[REDACTED]

[REDACTED]

VI. STUDY PROCEDURES

We will select sixty participants that have burn injury and meet the inclusion criteria proposed. Study visits will take place at either Spaulding Rehabilitation Hospital (SRH) or Spaulding Rehabilitation Network Research Institute (SRN-RI). Subjects will be thoroughly informed of their study visit location prior to enrollment.

Please note: for subjects who enroll as inpatient into the study, we will coordinate with the appropriate care outlets to ensure that the procedures of the study will not interfere with their standard of care. This includes, but is not limited to: physicians, therapists and nurses working with the patient. We will schedule inpatients as their clinical schedule allows – preferably after 3pm – unless the patient specifies otherwise. We will also attempt to target patients toward the end of their rehab stay when they are less medically complicated (ex. fewer changes in medications/treatments etc.) and may be more independent in their travel. When possible/feasible, we will also complete study visits in the patients’ room in order to limit time off of the floor.

Subjects will receive either (i) active tDCS; or (ii) sham tDCS in a randomized double blind design. Randomization assignment will be kept in a locked cabinet accessible only to the unblinded study investigator.

The study will occur in three parts, where the subject consents to Part I (Visit 1), then if they choose to continue, they may consent to Part II (Visits 2-14). After completion of Part II, they may then choose to consent to Part III (Visits 15-23).

[REDACTED]

[REDACTED]

[REDACTED]

[REDACTED]

[REDACTED]

[REDACTED]

[REDACTED]

[REDACTED]

[REDACTED]

[REDACTED]

[REDACTED]

[REDACTED]

[REDACTED]

[REDACTED]

[REDACTED]

[REDACTED]

[REDACTED]

[REDACTED]

[REDACTED]

[REDACTED]

[REDACTED]

[REDACTED]

[REDACTED]

[REDACTED]

[REDACTED]

[REDACTED]

[REDACTED]

[REDACTED]

[REDACTED]

[REDACTED]

[REDACTED]

[REDACTED]

[REDACTED]

[REDACTED]

DESCRIPTION OF ASSESSMENTS

Demographic Assessment: We will record the following baseline characteristics: age, sex, race/ethnicity and level of education.

VAS for Anxiety: This is a self-evaluation scale that ranges from 0 to 10, where 0 means no anxiety and 10 means the worst anxiety ever. This scale is used extensively in our tDCS studies [46, 54-56, 60, 62].

Modified Brief Pain Inventory (BPI) – main outcome: The BPI is a short self-assessment questionnaire that provides information on various dimensions of pain including how pain developed, the types of pain a patient experiences, and time of day pain is experienced, as well as current ways of alleviating pain [83]. The BPI also consists of the VAS Pain scale, a simple 10-point scale (0 = “no pain”, 10 = “pain as bad as you can imagine”) measuring a patients’ worst pain and least pain, on average and at present time. The Brief Pain Inventory provides information on the intensity of pain (the sensory dimension) as well as the degree to which pain interferes with function (the reactive dimension). According to several previous studies on pain in spinal cord injury, the BPI is an effective measure, as shown by both our group [54] and other studies [84]

Itching Severity: We will measure severity of itching using a VAS for itching severity. This is a 0 to 10 scale, where 0 indicates no intensity and a 10 indicates unbearable intensity of itching. This scale has been previously used in a study investigating treatment of refractory itching in burn patients. We will also have subjects keep a record of itching/pain severity using this scale in a diary through visit 12.

Itching Activity: We will also measure scratching activity using VAS for scratching activity. This is a 0 to 10 scale, where 0 indicates no activity of scratching and a 10 indicates frequent scratching activity. This scale has been previously used in a study investigating treatment of refractory itching in burn patients. We will also have subjects keep a record of itching/pain activity using this scale in a diary through visit 12.

5-D Itch scale: We will use this scale to measure five dimensions of itch: degree, duration, disability, and distribution. It is a valid and reliable for measuring itch and changes in itch over time

Beck Depression Inventory (BDI): The Beck Depression Inventory (BDI) is a 21-item test presented in multiple-choice format that measures the presence of and the degree of depression in adults [85]. If an enrolled subject gives a response of a of 1, 2 or 3 on question 9 on the BDI, the subject will be withdrawn from the study and the medical coverage will be contacted immediately by research staff to provide further evaluation and action to protect the subject (i.e. if the subject needs to be escorted or referred to the MGH ED Acute Psychiatry Service).

Impact of Event Scale Revised (IES-R): This 22-item scale is designed to measure severity of PTS symptoms associated with a traumatic event. These symptoms correspond to the symptoms

contained within the DSM-IV. Subjects are asked to rate their level of distress associated with the event on a 0-4 scale (0 means not at all distressed, 4 means extremely distressed). This scale has been extensively validated[86]

[figure not shown]
Veterans RAND 36 Item Health Survey (VR-36): The VR-36 was developed by our collaborators [87]. This survey was developed from the Veterans Health Study and includes both physical and psychological domains as a measure of overall quality of life. There are eight domains total including: bodily pain, role limitations due to physical problems, physical functioning, general health perception, vitality, social functioning, and role limitations due to mental health issues. This measure is valid and reliable[87].

Community Integration Questionnaire (CIQ): This instrument measures home integration competency, social integration, and productive activity[88]. It assesses levels of independence and interdependence. It includes questions about leisure activities, social interactions, travel/mobility, and daily activities; it contains a rating scale of how easily these items are accomplished (i.e. often/never, done alone/done with someone else, full time/not applicable). This assessment has been validated for use[88].

Primary and Secondary Employment Status: As part of the vocational sub-aim of this study, we will assess the employment status, and in particular the intention to seek employment, of each subject. Codes include: unemployed, unemployed but searching for work, part time or full time student, employed, or retired. These are the same employment rating scale codes used already in the model systems database.

Sleep Assessments: We will measure sleep outcomes using the Pittsburgh Sleep Quality Index, Insomnia Severity Scale, and VAS for sleep. We will also have the subjects keep a very short diary looking at sleep for the first 4 weeks of the study.

Medication Use Questionnaire and Diary: We will obtain a medication use history at study entry using a standardized questionnaire similar to that used in our prior tDCS studies, and update this information at each subsequent visit. We will also monitor patient medication throughout the course of the study using a subject Medication Diary. Participants will be required to record medications daily in a pain medication diary. Participants will be instructed to keep the pain medication diary throughout the baseline, treatment, and follow-up period. This diary will be maintained until completion of the study.

[figure not shown]

VII. STATISTICAL ANALYSIS

As study outcomes will be measured at baseline and several timepoints up to 12 months (post-enrollment), continuous and categorical outcomes will be analyzed by methods of longitudinal analysis using generalized estimating equations with an unrestricted covariance matrix, to estimate model parameters and test hypotheses. Tests of equality of the change from baseline to 12 months in the two treatment groups will be based on the estimate of the time (12 months versus baseline) by treatment interaction. This will allow participants who are seen at some follow-up visits but not at 12 months to contribute to the analysis. Time to event variables such as time to return-to-work will be analyzed by proportional hazards regression and Kaplan Meier estimation of time to event distributions.

Midway through the study, a power analysis will be performed to reassess the sample size needed to successfully complete this project. In this analysis, we will only look at the variability parameters (variance) and compare it to the one estimated before the study. We will not look at the effect estimates and therefore do not anticipate Type I error increase. This power analysis will be performed by a staff member (Co-Investigator) not involved with the analysis and conduct of the study. All blinded staff members will remain blinded.

The primary endpoint for this study is pain intensity as measured by the BPI. The study will have three secondary endpoints: itch as measured by the VAS scale, depression as measured by BDI and neural activity changes measured by somatosensory ERPs. These secondary outcomes represent three domains in which tDCS are anticipated to be effective. The same analytic approach will be employed in the analysis of the primary and secondary outcomes. For the outcomes, exploratory univariate analysis comparing active vs. placebo tDCS will be conducted. If a significant treatment effect is detected, similar adjusted longitudinal regression analysis will be performed; however these analyses will be considered hypothesis generating a p values interpreted cautiously given the increased likelihood of a false positive result given the false positive problem.

[REDACTED]

[REDACTED]

[REDACTED]

[REDACTED]

[REDACTED]

[REDACTED]

[REDACTED]

[REDACTED]

[REDACTED]

[REDACTED]

[REDACTED]

[REDACTED]

[REDACTED]

[Redacted]

[Redacted]

[Redacted]

[Redacted]

[Redacted]

[Redacted]

[Redacted]

[Redacted]

[Redacted]

[Redacted]

[Redacted]

[REDACTED]

[REDACTED]

[REDACTED]

[REDACTED]

[REDACTED]

[REDACTED]

[REDACTED]

XI. REFERENCES

2. Schneider, J.C., et al., *A descriptive review of neuropathic-like pain after burn injury*. J Burn Care Res, 2006. 27(4): p. 524-8.
3. Holavanahalli, R.K., P.A. Helm, and K.J. Kowalske, *Long-term outcomes in patients surviving large burns: the skin*. J Burn Care Res, 2010. 31(4): p. 631-9.
4. Malenfant, A., et al., *Prevalence and characteristics of chronic sensory problems in burn patients*. Pain, 1996. 67(2-3): p. 493-500.

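### Does optional consent to Part III mean that the 12-month between-arm test is observed only in volunteers?

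*Combined protocol and SAP*

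**What the plan says.** Section VI (Study Procedures) describes staged consent. Part I is Visit 1. Part II is Visits 2-14, for those who agree to continue. For the last part it says: "After completion of Part II, they may then choose to consent to Part III (Visits 15-23". The text that follows, up to the Description of Assessments, is redacted.

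Section VII (Statistical Analysis) states that "study outcomes will be measured at baseline and several timepoints up to 12 months (post-enrollment". It bases "Tests of equality of the change from baseline to 12 months in the two treatment groups" on the time-by-treatment interaction in a GEE model with unrestricted covariance. It adds: "This will allow participants who are seen at some follow-up visits but not at 12 months to contribute to the analysis". For the endpoints, with BPI pain as primary, it says: "The same analytic approach will be employed in the analysis of the primary and secondary outcomes".

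There are two timing clues, both for diaries. In the Description of Assessments, subjects "keep a record of itching/pain severity using this scale in a diary through visit 12", and a sleep diary covers the first 4 weeks. Neither is tied to a calendar date for Visit 14 or for any Part III visit.

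**The concern.** Part III is the last numbered block of visits, it is optional, and it opens only once Part II is finished. Month 12 is the latest outcome time that the plan names, and the 12-month interaction is the only between-arm test in the visible text with a stated time point. Put together, these suggest that the last visits hold the last outcome. The 12-month values for the primary endpoint would then depend on a second decision, made after randomisation and after the participant has experienced the treatment.

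Two things would be at stake. If opting in depended only on pain already recorded in Part II, the contrast would mainly lose precision. If it depended on later pain that nobody recorded, the contrast would be biased in an unknown direction, and the data could not reveal it. An obvious response would be to collect a short remote 12-month score from everyone who declines Part III.

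**Working it through.** **Step 1: does the text place month 12 in Part III?**

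| Item | What the visible text gives |
|---|---|
| Part II | Visits 2-14, no calendar dates |
| Part III | Visits 15-23 (nine visits), optional, no dates, no stated purpose |
| Outcome window | Up to 12 months after enrolment, no visit number |
| Symptom diary | Ends at Visit 12 |
| Sleep diary | First 4 weeks, no visit number |
| Follow-up of people who decline Part III | Nothing visible; redaction follows the consent sentence |

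At least three arrangements fit these facts:

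1. Month 12 is a Part III visit.
2. Part II runs to month 12, and Part III is an extension outside the randomised comparison.
3. Month 12 is collected by a route that does not depend on Part III consent.

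The argument for the first is that, if Visit 14 were month 12, all nine Part III visits would lie beyond the stated window. That counts against the second arrangement only if Part III visits must be outcome visits for the Section VII test, which the text does not say. The diary clues do not decide it either. The symptom diary stops at Visit 12, so Visits 13 and 14 remain in Part II with no date, which is compatible with long-term follow-up there.

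**Step 2: what does the analysis do with people who have no 12-month value?** Section VII foresees them and keeps their other visits. In a large-sample simulation (assumed: true effect 0.72 SD, correlation 0.5-0.7, opt-in related to outcome in the sham arm only, uptake 62-65%), a joint model with unrestricted covariance returned 0.72 SD when opt-in depended on the observed Part II response. An analysis of 12-month completers alone gave 0.51-0.57 SD. When opt-in depended on the unobserved 12-month value, the joint model gave 0.48-0.55 SD.

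**Step 3: size, if the premise were true.** The plan states no figure to reproduce. Only the total of 60 comes from the documents (Section IV); everything else is assumed: 30 per arm, equal correlation rho between visits, k earlier visits seen in everyone, and uptake p unrelated to outcome.

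Variance ratio = 1 + (1 − R²)(1/p − 1) / (2(1 − rho)), with R² = k·rho² / (1 + (k − 1)·rho).

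Example with rho = 0.3, k = 3, p = 0.5: R² = 0.27/1.6 = 0.169. The ratio is 1 + 0.831 × 1/1.4 = 1.59, so the standard error ratio is 1.26.

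| Uptake | SE increase by formula (rho 0.3-0.7, k = 3 or 5) | SE increase in simulated trials of 60 |
|---|---|---|
| 90% (54 seen) | 3-4% | 3-4% |
| 70% (42 seen) | 12-13% | 13-16% |
| 50% (30 seen) | 25-28% | 30-34% |

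These compare with all 60 seen at 12 months, which no follow-up scheme guarantees. If 85% could be reached by any means (assumed), the same formula puts the avoidable part at about 6-7% for 70% uptake and 19-22% for 50%.

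Bias in the contrast (active minus sham) = −(1 − pA)·dA + (1 − pS)·dS, where d is how much worse decliners' pain is than the model infers. With d = 1 point in one arm only, the size is 0.1, 0.3 or 0.5 points at 90%, 70% or 50% uptake. With d = 1 in both arms it is 0 at equal uptake, and 0.5 − 0.3 = 0.2 points at 70% versus 50%. These figures are an assumed non-uptake multiplied by an assumed gap; they estimate nothing about this trial.

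**The case for a change.** The strongest case for the concern is that it can be put as a conditional, and the conditional is sound. Part III is optional, the 12-month test covers the primary endpoint, and if month 12 is a Part III visit then its values exist only for those who opt in. Placing the last outcome in the last block is a natural reading. Keeping decliners' earlier visits does not show what their 12-month pain was, as the last simulation result confirms, and standard GEE gives less protection than a correctly specified joint model. The visible text has no sensitivity analysis for people who decline Part III. A telephone or mail score would be cheap.

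The logic and the arithmetic stand. The premise is not established. It needs both a date and a purpose for Part III, and both would normally appear in the text that is blacked out. The missing sensitivity analysis carries little weight for the same reason: long redactions also follow Section VII. What remains is that values missing for unobserved reasons cannot be tested, and that applies to any trial with attrition by month 12.

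Nor can a remote score be shown to help. It might duplicate follow-up that the redacted schedule already contains. It might also pool decliners with people who underwent unknown Part III procedures.

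**Conclusion.** The concern does not hold. The public text supports only that month 12 may lie in Part III, not that it does or probably does. A block entered after Part II is complete could equally be an extension outside the randomised comparison. The plan already expects participants without a 12-month visit and uses a longitudinal model in which their other visits count.

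No size can be attached. The 3-4% to 25-34% rise in standard error and the 0.1 to 0.5 point shifts rest on assumed uptake, correlation, number of earlier visits, allocation and gap, and all of them also require the unproven premise. Asking which Part holds month 12 would be asking for detail that the redacted schedule may well give, and that is not a flaw in the plan. This conclusion rests on the visible text alone. An unredacted schedule that put month 12 in Part III, with no other follow-up of people who decline it, would reopen the question.

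### Does a pain test fixed only at 12 months leave Aim 1 without a planned comparison nearer to treatment?

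*Combined protocol and SAP*

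**What the plan says.** Section VII plans a GEE analysis with unrestricted covariance for outcomes measured at baseline and at several later times, the last being 12 months after enrolment. "Tests of equality of the change from baseline to 12 months in the two treatment groups" rest on the 12-months-versus-baseline by treatment interaction. On incomplete follow-up it adds: "This will allow participants who are seen at some follow-up visits but not at 12 months to contribute to the analysis".

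The same section states: "The primary endpoint for this study is pain intensity as measured by the BPI". It continues: "The same analytic approach will be employed in the analysis of the primary and secondary outcomes". The 12-month interaction therefore governs pain. An active-versus-placebo univariate comparison is also planned; it is labelled exploratory and has no time point.

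Aim 1 in Section II is untimed: "Our first hypothesis is that active tDCS will be associated with a larger pain or itching reduction assessed by BPI and Itch VAS/5-D".

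Section VI divides participation into Part I (Visit 1), Part II (Visits 2-14) and Part III (Visits 15-23), each with its own consent. Part III is optional: "After completion of Part II, they may then choose to consent to Part III (Visits 15-23"). The medication diary entry under Description of Assessments separates treatment from follow-up: "Participants will be instructed to keep the pain medication diary throughout the baseline, treatment, and follow-up period".

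**The concern.** Aim 1 asks whether active tDCS reduces pain or itching more than sham, and the natural reading is an effect during or soon after treatment. The one timed test sits at the last outcome time. If benefit fades, that test can be null when the treatment worked for a while, and a null result would not separate a treatment that never worked from one whose effect wore off. The exploratory comparison does not settle this, because its time point could be chosen after the data are seen.

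The consent structure seems to make matters worse. If the 12-month visit belongs to Part III, pain at 12 months is observed only in those who agreed to continue. The main test would then lose power and might be distorted by who stays.

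**Working it through.** **Text.** The visible between-arm comparisons are:

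| Place | Comparison | Time point |
|---|---|---|
| Section II, Aim 1 | Pain or itch reduction, active vs sham | None |
| Section VII, GEE | Time-by-treatment interaction | 12 months vs baseline |
| Section VII, primary endpoint | BPI pain intensity | None in that sentence; same approach applies |
| Section VII, univariate analysis | Active vs placebo, exploratory | None |

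So the observation about the visible text is correct. Three further links are needed before it becomes a flaw, and none is visible:

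- *That 12 months falls in Part III.* No visible text assigns a month to a visit. The symptom diary runs through visit 12, the sleep diary covers the first 4 weeks, and Part II ends at Visit 14. None of these locates 12 months.
- *That stimulation ends within Part II.* The stimulation schedule is redacted.
- *That no hidden text names an earlier contrast.* Section VII refers to a variance estimated before the study, which appears nowhere visible. The last visible citation is number 88, yet references 89 and 90 are a structural equation modelling handbook and a mediation analysis review. Further analysis text probably exists.

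**Size, for illustration.** The only design figure visible is 60 participants. Everything else is assumed: 30 per arm; two-sided 5% test; SDs of 1.6, 2.3 and 2.5 at baseline, end of Part II and 12 months; correlations 0.5 (baseline, end of Part II), 0.4 (baseline, 12 months) and 0.6 (end of Part II, 12 months).

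1. SD of change to 12 months: √(2.56 + 6.25 − 2×0.4×1.6×2.5) = √5.61 = 2.369. To end of Part II: √(2.56 + 5.29 − 2×0.5×1.6×2.3) = √4.17 = 2.042.
2. Standard error of the between-arm difference, SD×√(2/30): 0.612 at 12 months and 0.527 at end of Part II.
3. 80% power at 30 per arm needs a standardised difference of 0.7356, that is 0.7356×2.369 = 1.742 points.
4. With 30% missing at random at 12 months, R² from the two earlier values is (0.16 + 0.36 − 2×0.4×0.6×0.5)/(1 − 0.25) = 0.373, and the residual variance is 6.25×(1 − 0.373) = 3.917. The standard error is √{(2/30)×[5.61 + 3.917×(1/0.7 − 1)]} = 0.697. Power at the full effect falls from 80% to 69%.
5. If the 12-month effect is half (0.871 points), power is 29% with complete data and 23% with 30% missing. Power for 1.742 points at end of Part II is 90%.
6. Covariance of the two estimates: (2/30)×(2.56 − 1.84 − 1.60 + 3.45) = 0.171, a correlation of 0.53 (0.47 with 30% missing). Joint simulation then gives:

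| 12-month effect as share of 1.742 | Null at 12 months, earlier interval excludes zero (complete / 30% missing) |
|---|---|
| Full | 15% / 25% |
| Three quarters | 36% / 47% |
| Half | 62% / 68% |
| Quarter | 80% / 81% |

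The range follows the assumed decay, on which the documents give no figure.

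**What a sequential earlier test would add.** Placed after the 12-month test, it is reached only when that test succeeds. In the half-effect case with complete data, both succeed in 28% of trials, and 28% + 62% = 90% recovers the earlier contrast's power. The 62% is exactly the set in which the earlier test is never reached. What those trials gain is an estimate with a 95% interval of about ±1.06 points (2.00×0.527). The planned model with time as categories already produces such an interval at each measured visit.

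**Selection at 12 months.** If continuation follows relief already observed, simulated bias under the stated covariance structure is 0.01 to 0.06 points, at most 0.063/0.697 = 0.09 standard errors. If patients foresee a quarter of the otherwise unpredictable variation, the effect shrinks by 0.02 to 0.10 points (0.098/0.697 = 0.14 standard errors). Complete foresight gives up to 0.23, an extreme bound because consent precedes the 12-month value.

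**The case for a change.** The best case for a change is that the main weakness does not depend on Part III. Wherever 12 months falls, no earlier timed contrast is visible, and a trial meant as a first step towards a new therapy should be able to tell an effect that faded from one that never occurred. Naming one contrast would cost a sentence, leave the 12-month test as it stands, and remove the freedom to choose a favourable visit later. Moreover, GEE in general relies on data missing completely at random, and each point by which decliners in one arm differ from the model's prediction would move the estimate by 0.30×1 = 0.30 points (0.43 standard errors) with 30% missing.

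Some of this stands. The visible text names no earlier time point, and a stated visit would limit selective emphasis. The rest does not carry. What was lost to redaction cannot be counted as absent. The multi-visit model with unrestricted covariance is most naturally fitted with categorical time, so an analyst reporting it would show the treatment difference at the earlier visits as a matter of course. Whether a BPI is taken at the end of Part II cannot be seen. The missing-data argument presumes that 12 months lies in Part III and that decliners depart from prediction, while the simulated selection bias is small under all but extreme assumptions. A 12-month test of lasting benefit is also a legitimate choice.

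**Conclusion.** No change to the plan follows. It is true that 12 months is the only time point attached to a between-arm pain test in the visible text. It is not shown that this conflicts with Aim 1, that the 12-month visit is in the optional Part III, or that the full document lacks an earlier contrast. The 15% to 81% range rests wholly on assumed SDs, correlations, effect size and decay; it shows that timing could matter, not that this plan has it wrong. An earlier contrast tested after the 12-month one would supply no formal test in the trials where harm is claimed, and its interval is available from the model already planned, if time is categorical as the wording suggests. The remaining point is the name of a visit, a detail that analysts can fill sensibly and that hidden text may already contain.

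### As ordinarily read, the main test is a change-score contrast with the baseline slope fixed at 1: valid under randomisation, but stating a baseline adjustment could gain precision at little cost

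*Combined protocol and SAP*

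**What the plan says.** Section VII (Statistical Analysis) treats baseline as one of the repeated measurements and analyses outcomes by "generalized estimating equations with an unrestricted covariance matrix". The test of treatment on the baseline-to-12-month change "will be based on the estimate of the time (12 months versus baseline) by treatment interaction". Participants with some follow-up but no 12-month visit are meant to contribute.

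The primary endpoint is BPI pain intensity; the secondary endpoints are itch VAS, BDI and somatosensory ERPs. For these, "The same analytic approach will be employed in the analysis of the primary and secondary outcomes".

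Adjustment appears once: "If a significant treatment effect is detected, similar adjusted longitudinal regression analysis will be performed". No covariate is named there, and the section treats those results as hypothesis generating. Midway through the study the sample size is reassessed, and for this "we will only look at the variability parameters (variance) and compare it to the one estimated before the study". The readable text does not say which variance is meant: 12-month score, change score or residual.

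No readable sentence gives the arms a common baseline mean or makes baseline score a covariate in the main test. Much of the document is redacted, including text after the analysis section.

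**The concern.** A model with treatment, visit and their interaction subtracts the whole baseline score from the 12-month score. The most precise use of baseline is normally a fitted slope, and 1 is the best slope only by coincidence. Any distance from the best slope adds variance in proportion to the square of that distance.

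With 60 participants, avoidable variance means lower power or wider intervals for BPI pain and, through the shared approach, for the three secondary endpoints. The mid-study reassessment could restore power, but only by enrolling more people. The information that would remove the excess, the baseline score, is already collected. The conditional adjusted analysis does not help, because it runs only after a significant result and is not the main test.

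**Working it through.** **Inputs from the documents.** Section IV: "We will select 60 subjects that have burn injury and meet the following criteria". Section VI: "Subjects will receive either (i) active tDCS; or (ii) sham tDCS in a randomized double blind design". How 60 was reached, the allocation ratio, ρ, the SDs, drop-out, alpha and power are not readable, so 60 cannot be reproduced. Everything below about these quantities is assumed.

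**What the test estimates.** With a separate baseline mean per arm and complete data, the interaction equals the difference in mean change, whatever the working covariance. A GEE fit to simulated data confirmed this: −0.2343 by both routes.

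**Large-sample cost, equal arms.** Let k = baseline SD / 12-month SD, and work in units of the 12-month variance.
- Change score: 1 + k² − 2ρk
- Baseline-adjusted: 1 − ρ²
- Saving: (k − ρ)² / (1 + k² − 2ρk), which is (1 − ρ)/2 when k = 1

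Example, k = 1 and ρ = 0.5: change 1 + 1 − 1 = 1.00; adjusted 1 − 0.25 = 0.75; saving 25%.

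| k | ρ 0.2 | ρ 0.5 | ρ 0.7 | ρ 0.8 |
|---|---|---|---|---|
| 0.7 | 21% | 5% | 0% | 3% |
| 1.0 | 40% | 25% | 15% | 10% |
| 1.3 | 56% | 46% | 41% | 41% |

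The direction of k is unknown. Section IV requires a score of at least 4, which may narrow the baseline pain SD. But itch alone can meet it, and itch-only entrants may widen that SD.

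**In participants.** To match 60 analysed with adjustment, the change-score test needs 60/(1 − saving): 60/0.60 = 100, 60/0.75 = 80 and 60/0.90 = 67 at k = 1 (ρ 0.2, 0.5, 0.8). It needs 136 at k = 1.3, ρ 0.2, and 60 at k = 0.7, ρ 0.7.

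**In power.** Assume ρ 0.5, 30 per arm, two-sided 0.05 and an effect of 0.6 of the 12-month SD. The change score gives 73%, 63% and 49% at k = 0.7, 1.0 and 1.3; adjustment gives 74% throughout.

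**With 30% lost by 12 months**, unrelated to outcome, under several visit and correlation patterns:

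| k | ρ 0.2 | ρ 0.5 | ρ 0.8 |
|---|---|---|---|
| 0.7 | 15–18% | 4–5% | 2–3% |
| 1.0 | 32–36% | 19–23% | 7–9% |
| 1.3 | 47–51% | 37–43% | 33–39% |

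**Small-sample price.** Estimating the slope inflates variance by about 1 + 1/56 = 1.018 at 30 per arm. Simulated adjusted-to-change variance ratios at k = 1 were 0.613, 0.758 and 0.909 (ρ 0.2, 0.5, 0.8), close to the formula. At k = 0.7, ρ 0.7, where nothing can be gained, adjustment was about 2–3% worse.

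**A common baseline mean under GEE.** If the software fits an unstructured correlation with one variance for all visits, the implied slope is ρ, not the best slope ρ/k. The variance at slope b is 1 − 2bρk + b²k².
- k = 0.7, ρ = 0.7, b = 0.7: 1 − 0.686 + 0.240 = 0.554, against 0.51 for the change score: 8.6% worse.
- k = 0.7, ρ = 0.8, b = 0.8: 1 − 0.896 + 0.314 = 0.418, against 0.37: 12.9% worse.

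Simulations at 30 per arm gave ratios of 1.10 at ρ 0.7 and 1.09 to 1.12 at ρ 0.8.

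**Unequal allocation.** At 1:1 a pooled slope targets the best slope. At 2:1 it misses by one third of the difference between the arms' slopes. In an extreme assumed case (larger arm ρ 0.2, SD 1.0; smaller arm ρ 0.95, SD 1.2; baseline SD 1) the arm slopes are 0.20 and 1.14. The pooled slope is 0.513 and the best slope 0.827. Relative to the change score, large-sample variance is 1.106 with the pooled slope and 0.953 with arm-specific slopes; simulation at 40/20 gave 1.146 and 0.966.

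**The case against.** The planned test is legitimate and answers the question Section VII poses. This stands. Because randomisation equalises the expected baseline means, an adjusted 12-month difference targets the same treatment effect, so the choice concerns precision only.

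Section VII never says that a treatment term is fitted at baseline. A model with a common baseline mean also tests treatment through a visit-by-treatment interaction, so the quoted words fit it too. This also stands, and it is why the point is confined to the ordinary reading. Redacted text may likewise contain the adjustment, the allocation ratio or the planning variance; their absence from the readable text is not an error in the plan.

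The gain may be nil, or slightly negative at this sample size. That is correct where k is close to ρ. The loss there is about 2–3%, against 25% saved at ρ 0.5 with equal SDs.

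A reader might infer that, because an unrestricted covariance is already planned, removing the baseline treatment term is all that is needed. The documents do not support this. They name GEE, and do not say whether the variance is free at each visit. With one common variance, that change can make the test less precise than the planned one. If the variance is truly free by visit, the difficulty goes away.

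**Conclusion.** The concern holds as a cheap improvement, on efficiency only and with medium confidence. It rests on the ordinary reading of the interaction and on no redacted sentence supplying the adjustment.

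Two stronger readings should be resisted.
- A reader might infer that the trial wastes up to 56% of its sample. That figure is the top of an assumed grid and needs ρ 0.2, a baseline SD 30% above the 12-month SD and complete data. It is not a bound from the documents: with k = 1 and the same ρ range the ceiling is 40%, with k up to 1.5 it is 64%, and with 30% drop-out on the original grid it is 51%.
- A reader might infer that the test is biased or invalid. It is unbiased under randomisation with complete data. With drop-out, unweighted GEE needs stronger missing-data conditions, but that is a separate matter from the baseline slope.

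**What to change.** Before unblinding, state the mean model for BPI, itch VAS, BDI and ERPs: the same longitudinal model, with post-baseline visits as outcomes, baseline score and baseline-by-visit as covariates, and the treatment effect tested at 12 months. Participants with follow-up visits but none at 12 months still contribute.

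- A common-baseline-mean model (no treatment term at baseline, treatment-by-visit terms kept) is acceptable only if the variance is estimated separately at each visit. If this is already intended, say so, including the visit-specific variances.
- If allocation is not 1:1, use arm-specific baseline slopes with baseline centred at the overall mean.
- Base the mid-study variance reassessment on the variance that matches the chosen estimator, and restate the pre-study variance on the same basis. With equal SDs, sizing the adjusted test from a change-score variance overstates the sample by 1/0.60 = 1.67, 1/0.75 = 1.33 or 1/0.90 = 1.11 times at ρ 0.2, 0.5 or 0.8.

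The cost is SAP wording and no new data. The statistical price is about 2% of variance at 30 per arm, or about 3% for arm-specific slopes at 40/20, and it is a net loss only where the true gain is near zero. No bias arises provided baseline is measured before the first stimulation.
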